#### 11.14 Natural products known to modulate estrogens

The following herbal supplements have been associated with hormonal activity. The primary endpoint, mammographic density, is positively correlated with estrogen levels. Therefore, subjects will be asked to avoid these items before during the treatment period. Any use will be recorded along with medication changes during the course of the trial.

- |                                  |                                       |
|----------------------------------|---------------------------------------|
| • Alfalfa                        | • Isoflavones                         |
| • Bee Pollen                     | • Kava                                |
| • Black Cohosh                   | • Kudzu                               |
| • Blue Cohosh                    | • Licorice                            |
| • Cats Claw                      | • Lignans                             |
| • Chasteberry                    | • Passionflower                       |
| • Chysin                         | • Propolis                            |
| • Coumestans                     | • Red clover or other clover extracts |
| • Cramp Bark                     | • Sarsaparilla                        |
| • Dong Quai, or Chinese Angelica | • Saw palmetto                        |
| • DHEA                           | • Shepherds purse                     |
| • Evening Primrose               | • Soy extracts                        |
| • Feverfew                       | • St. Johns Wort                      |
| • Flaxseed                       | • Valeriana                           |
| • Ginseng                        | • Wild yam                            |
| • Hops                           |                                       |

#### 11.15 Drugs described to modulate CYP2D6

The following drugs have been reported as inhibitors or inducers of CYP2D6, which is the major P450 enzyme that metabolizes tamoxifen. Concomitant use of strong and clinically significant moderate inhibitors will not be allowed while on trial. Other moderate inhibitors should be avoided while on study.

***Strong CYP2D6 inhibitors  
(not allowed on study):***  
 bupropion (Wellbutrin)  
 fluoxetine (Prozac)  
 paroxetine (Paxil)  
 quinidine (Quinidex)

***Clinically significant moderate CYP2D6 inhibitor  
(not allowed on study):***  
 duloxetine (Cymbalta)

***Other moderate CYP2D6 inhibitors***

**(should be avoided while on study):**

sertraline (Zoloft)  
terbinafine (Lamisil)

**Weak CYP2D6 inhibitors (will be tracked on study):**

amiodarone (Cordarone)  
cimetidine (Tagamet)  
thioridazine (Mellaril)

**Possible CYP2D6 inhibitors (will be tracked on study):**

celecoxib (Celebrex)  
chlorpheniramine\*  
chlorpromazine (Thorazine)  
citalopram (Celexa)  
clemastine (Tavist)\*  
clomipramine (Anafranil)  
diphenhydramine (Benadryl)\*  
doxepin (Sinequan)  
doxorubicin (Adriamycin)  
escitalopram (Lexapro)

\*available over the counter

\*\*examples: cetirizine (Zyrtec), dimenhydrinate (Dramamine), doxylamine (included in NyQuil), fexofenadine (Allegra), loratidine (Claritin), meclizine (Antivert, Dramamine [less drowsy formulation]), pheniramine (Avil)

halofantrine (Halfan)  
haloperidol (Haldol)  
hydroxyzine (Vistaril, Atarax)\*  
levomepromazine (Nozinan)  
methadone  
metoclopramide (Reglan)  
midodrine (ProAmantine)  
moclobemide (Aurorix, Manerix)  
perphenazine (Trilafon)  
ranitidine (Zantac)\*  
ritonavir (Norvir)  
ticlopidine (Ticlid)  
tripelennamine (Pyribenzamine)  
other histamine H1 receptor antagonists\*\*

**Possible CYP2D6 inducers (will be tracked on study):**

dexamethasone (Decadron, Hexadrol)  
rifampin (Rifadin, Rimactane)

**Virtually no effect on CYP2D6:**  
venlafaxine (Effexor) – *preferred antidepressant while on study*

#### 11.16 Other drugs to avoid while on trial

- Warfarin or other coumarin-type anticoagulants
- Systemic exogenous hormonal agents, including
  - Other selective estrogen receptor modifiers, such as raloxifene (Evista).
  - Systemic hormone replacement therapy (includes oral or transdermal formulations). Vagifem and Estring, two formulations of locally applied vaginal estrogen associated with minimal systemic absorption, may be allowed.

Other estrogen-containing vaginal creams, while not an exclusion, should be avoided whenever possible. Patients with a history of hormone modifying herbal supplements (see section 11.3) are eligible, but patients will be asked to avoid their use after on study.

- Hormonal forms of contraception (includes oral, transdermal, implanted, and injectable formulations),
- Aromatase inhibitors,
- GnRH analogs,
- Prolactin inhibitors, and
- Androgens or antiandrogens.

## 12.0 STATISTICAL CONSIDERATIONS

### 12.1 Study design

This is a Phase IIb randomized placebo controlled clinical trial.

### 12.2 Accrual plan

This study is expected to accrue 230 evaluable subjects.

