## Schema

# Low Dose Tamoxifen for Radiation-Induced Breast Cancer Risk Reduction

230 patients will be randomized 1:1 to take a tablet containing 5mg tamoxifen (TAM) versus a placebo of equal size and shape daily for two years. The primary endpoint is mammographic density, which will be measured at baseline and on an annual basis (at Year 01 and 02). Blood and urine collections will also be scheduled annually for measurement of circulating markers of efficacy and safety. Normal breast tissue will be sampled before and after the two-year treatment course for measurement of tissue-based efficacy markers (breast tissue sampling by RPFNA no longer collected from patients).

[figure not shown]

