## 10.0 CRITERIA FOR EVALUATION AND ENDPOINT DEFINITIONS

A subject will be considered evaluable if they complete at least one year on the study, including both baseline and one-year study procedures. The outcome status (in terms of toxicity and biological response) of all eligible subjects will be reported. Subjects who begin treatment will be accounted for in the summaries of patient reported outcomes, regardless if they are considered evaluable or not.

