The expected RTMBD at the three time points in the pre-menopausal and post-menopausal women in the Puget Sound sample were estimated longitudinally using SAS Proc Mixed with a compound symmetry covariance structure. Square root transformation was used to normalize the distribution. A significant decline in MBD with time was detected. Since the covariance matrices of the pre- and post-menopausal women looked very similar, for simplicity, they were assumed to be equal. To determine the variance/covariances of the MBDs and the expected values at t0, t1, t2 in the anticipated CAYAC sample, 1000 random trials of size n were generated from multivariate normal distributions with parameters estimated from the Puget Sound sample to simulate the CAYAC sample expected to contain 67% pre-menopausal and 33% post-menopausal women. Sixty-seven percent of n were drawn randomly from a multivariate normal distribution with expected MBD of (24.7, 23.57, 22.27) at (t0, t1, t2) as predicted for Puget sound pre-menopausal women, and 33% of n were drawn randomly from a multivariate normal distribution with expected Y of (15.49, 11.99, 13.03) as predicted for post-menopausal women. For each of the 1000 simulated samples, a longitudinal linear model was fitted assuming a compound symmetry structure for the covariance. The average of the 1000 estimates of the linear parameter was used to estimate the expected RTMBD at t0, t1, t2 for the CAYAC control sample.

The expected RTMBDs for CAYAC controls obtained from simulations were used to specify the effect size, defined as the difference between expected values at t2 for the two groups divided by the common sd, in the longitudinal power calculations were conducted using the program RMASS2. [107]. We assumed a Type I error of .05, power of .80, 2-sided test, no attrition over time, linear trend, compound symmetry covariance structure, and a correlation of 0.8 between measurements (estimated from the Puget Sound sample).

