The size of the difference in MBD that can be detected between the low dose tamoxifen and placebo groups at year 2 (t2) are shown in the table below. Column 4 indicates the expected MBD before randomization (at t0). The expected MBDs at t2 for the control and treatment groups are shown in columns 5 and 6, respectively. Column 7 and Column 8 are the % reduction in MBD at t2 relative to t0 in the placebo control group and low dose tamoxifen treatment group, respectively. The last column shows the % reduction in PD in the treatment group at t2 relative to controls.

Placebo (PBO)	Low Dose Tamoxifen (LDTAM)	Power	Exp(MBD) at t0	Exp(MBD) at t2		% reduction in MBD at t2 relative to t0		% reduction in MBD at t2 for LDTAM group relative to PBO
			Both treatment groups	PBO	LDTAM	PBO	LDTAM	
50	50	.8	21.2	18.75	13.42	11.6%	36.5%	28.4%
		.9	"	"	12.68	"	40.0%	32.4%
75	75	.8	21.1	18.67	14.27	"	32.5%	23.5%
		.9	"	"	13.70	"	35.2%	26.6%
100	100	.8	21.2	18.72	14.89	"	29.6%	20.5%
		.9	"	"	14.32	"	32.3%	23.5%
150	150	.8	21.1	18.64	15.47	"	26.8%	17.0%
		.9	"	"	15.00	"	29.1%	19.5%
200	200	.8	21.1	18.67	15.91	"	24.8%	14.8%
		.9	"	"	15.50	"	26.7%	17.0%

If we anticipate the MBD in the low dose tamoxifen group to change from 21.1 at t0 to 14.89 at t2 compared to 18.72 at t2 in controls (in other words, a reduction of ~30% with low dose tamoxifen versus 11.6% with placebo over a 2 year time, or about 20% reduction in MBD with low dose tamoxifen relative to placebo, or an effect size of 0.25 at t2), a sample size of 100 per arm will be able to detect this magnitude of change with 80% power. With 10% attrition at each annual follow-up visit, 115 women per arm (or a total of 230) would be required. Thus, the goal accrual for this trial will be 115 women per arm, for a total of 230 women at t0.

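### Section 12.2 gives 230 as the number of evaluable women, but 230 is the number randomised; under the plan's own definition and attrition at most about 207 would be evaluable.

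*Combined protocol and SAP*

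**What the plan says.** - Section 12.2 (Accrual plan) consists of one sentence: "This study is expected to accrue 230 evaluable subjects".
- Section 10.0 defines the term: "A subject will be considered evaluable if they complete at least one year on the study, including both baseline and one-year study procedures". It separates these women from those who only begin treatment, who still enter the patient-reported summaries.
- The schema: "230 patients will be randomized 1:1".
- Section 12.5 finds 100 per arm sufficient for 80% power without attrition, then adds: "With 10% attrition at each annual follow-up visit, 115 women per arm (or a total of 230) would be required". It concludes: "Thus, the goal accrual for this trial will be 115 women per arm, for a total of 230 women at t0".
- Section 12.5, under adverse events, takes 94 women per arm at study end after the same yearly attrition.
- Section 4.0 gives 230 as the accrual goal and does not tie it to evaluability.

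**The concern.** The number 230 carries two meanings. In the schema and Section 12.5 it counts women at entry, before any loss. In Section 12.2, read with the definition in Section 10.0, it counts women who have completed a year. The two agree only if nobody is lost in year one, and Section 12.5 assumes that 10% are.

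What is at stake is the formal statement of trial size. Section 12.5 treats accrual as complete at 230 randomised. Section 12.2, taken literally, treats it as complete when 230 women meet the one-year definition. A final report with 230 randomised and about 207 evaluable would match the design exactly, yet would look like a shortfall against Section 12.2.

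**Working it through.** **Inputs**
- Two-sided alpha 0.05 and 80% power (Section 12.5: "We assumed a Type I error of .05, power of .80, 2-sided test, no attrition over time").
- Compound symmetry with "a correlation of 0.8 between measurements" (Section 12.5).
- Effect size 0.25 SD at t2 (Section 12.5).
- Attrition of 10% at each annual visit (Section 12.5), so retention is 1, 0.90 and 0.81 at t0, t1 and t2.
- Definition of evaluable (Section 10.0).

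**Step 1: reproduce the plan's 100 and 115 per arm, to establish what 230 counts.**

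With three equally spaced visits and compound symmetry, the linear contrast is t2 minus t0.

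- No attrition: contrast variance = 2 x (1 - 0.8) = 0.4 in SD squared. n per arm = 2 x (1.960 + 0.842)² x 0.4 / 0.25² = 2 x 7.849 x 0.4 / 0.0625 = 100.5. The plan says 100.
- With attrition: the plan names its program but does not print the formula. I assume the usual form for such programs, weighting each visit by 1/√retention. Contrast variance = 1/1 + 1/0.81 - 2 x 0.8 / √(1 x 0.81) = 1 + 1.2346 - 1.7778 = 0.4568. n per arm = 2 x 7.849 x 0.4568 / 0.0625 = 114.7, so 115 per arm and 230 in total. This matches the plan.
- If the first 10% were lost only at year two (retention 1, 1, 0.9), the same formula gives 106.6, which does not match. The plan's 115 therefore fits a 10% loss by the one-year visit.

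Other ways of allowing for attrition give somewhat different totals: 100/0.9 = 112, 100/0.81 = 124, and 119 to 120 for a mixed model with monotone dropout. All of them are numbers at entry. None turns 230 into a number of completers.

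**Step 2: expected evaluable number from 230 randomised.**

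- One year: 230 x 0.90 = 207 (103.5 per arm). Shortfall against Section 12.2: 230 - 207 = 23.
- Section 10.0 also requires the one-year procedures. The documents give no separate rate for retained women who miss them, and any such misses lower the count. So 207 is an upper figure at this attrition rate.

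**Step 3: check against the plan's own end-of-study number.**

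- 115 x 0.81 = 93.15 per arm, or 230 x 0.81 = 186 in total.
- Section 12.5 gives 94 per arm, or 188 in total. Rounding up each year reproduces it: 115 x 0.9 = 103.5, taken as 104; 104 x 0.9 = 93.6, taken as 94.
- The gap of 186 to 188 is rounding. Either way, Section 12.5 does not expect 230 women to remain.

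**The case against.** The strongest reply is that one word has slipped. The schema, Section 4.0 and Section 12.5 all use 230 as the overall target, Section 12.5 derives it openly with the attrition stated, and no calculation fails. That is right, and it locates the error in Section 12.2 rather than in the power calculation. It does not remove the error. Section 10.0 gives the word a specific meaning, and the sentence containing it is the whole accrual plan.

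Three stronger readings are tempting, and the documents do not support them.

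- *The trial is underpowered.* A reader might infer that 23 missing evaluable women cost power. Section 12.5 bases primary power on 230 at t0 with attrition allowed for. The primary analysis in Section 12.4 is intention-to-treat, includes every woman with baseline mammographic data, and accommodates incomplete follow-up. Section 12.4 does not use the Section 10.0 category to define an analysis set.
- *Sites are told to enrol past 230.* Section 12.2 states an expectation. It contains no replacement rule and no instruction to sites, and Section 12.5 fixes the goal at t0.
- *About 256 women should be randomised.* The arithmetic is correct (230/0.9 = 255.6), but it matters only if 230 evaluable women were truly intended, and the derivation in Section 12.5 shows that they were not.

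**Conclusion.** The point holds as an inconsistency in the formal accrual statement. Section 12.2 gives an evaluable size of 230; the design yields at most about 207 under the Section 10.0 definition, a difference of 23 women or 10%. Section 12.2 also conflicts with Section 12.5 on when accrual is complete.

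The figure of 207 rests on two assumptions: that the plan's 10% attrition applies by the one-year visit, which its wording says and Step 1 supports, and that every retained woman completes the one-year procedures. The second is optimistic, hence the words at most.

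The consequence is limited. Primary power and the primary intention-to-treat analysis do not change. This is a wrong sample-size figure in the statistical section that should be corrected, not a flaw in the design.

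**What to change.** Restate Section 12.2 along these lines: *230 women will be randomised (115 per arm); with 10% attrition at each annual visit, at most about 207 are expected to be evaluable as defined in Section 10.0.*

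If a two-year figure is added, align it with the 94 per arm in Section 12.5. Either carry 94 per arm (188 in total) into Section 12.2, or change both places to 93 per arm (186 in total), so that the correction does not create a new mismatch.

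The cost is one sentence and a less favourable stated evaluable number. Enrolment, power, procedures and analysis stay as they are.

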### 12.3 Stratified randomization

Central participant IDs will be generated by the coordinating center and will be issued to sites as they are activated. Participant IDs for all sites will be sent to Sharp Clinical Services, along with the site names and strata as defined below. Sharp Clinical Services designed a system (IWRS) that will manage blocked stratified randomization, with menopausal status (2 strata: pre- and post-menopausal), radiation dose to the chest (2 strata: 1200-2599 cGy,  $\geq 2600$  cGy), and age at radiation exposure (2 strata: <18y, 18-40y) as stratification factors (8 strata total) and a block size of 4 to balance the number of participants in each arm. Blinded study drug will be shipped to sites as they are activated by Sharp Clinical Services. Once a subject has completed all screening assessments and is eligible, the site CRA or CRN will randomize the subject to low-dose tamoxifen or placebo using the Sharp Clinical Services IWRS, which will assign a blinded study kit. This will generate an e-mail notification to the site and the coordinating center that randomization has been completed (as described in Section 9.3).

### 12.4 Data analytic plan

***Aim 1:** To determine the impact of low-dose tamoxifen on surrogate endpoint biomarkers of BC risk.*

**Mammographic breast density (MBD).** MBD is the ratio of absolute density to the total breast area. Since participants are randomized, we expect MBD to not differ by treatment status at baseline ( $t_0$ ). However, we will evaluate the success of randomization by examining between group differences in demographic and clinical characteristics (i.e. age, radiation dose, age at radiation exposure), study site, as well as the average MBD of the two breasts (or the available one) at baseline. If imbalance is evident, analysis will take into account the covariates with significant imbalance.

Using an intention-to-treat analysis, the efficacy of low dose tamoxifen in reducing MBD will be compared between patients in the low dose tamoxifen intervention and placebo group by applying the linear mixed effects model for bivariate normally distributed data [103]. All patients with a minimum of baseline ( $t_0$ ) mammographic data will be included in the analysis. MBD data from each breast will be square root transformed (RTMBD) to normality before model fitting. RTMBD for each breast will be modeled by the unstructured mean model using two indicator variables of time. We will assume the effects of time on RTMBD to be the same in both breasts by setting their coefficients equal. Correlation between the breasts will be introduced by assuming a bivariate normal random intercept model with a common fixed effects intercept and breast-specific random effects. Residual errors will be assumed to be bivariate normally distributed with mean zero and non-zero correlation. Unstructured and compound symmetry covariance structures will be considered for residual errors. The fixed effects intercept will be allowed to differ between treatment groups. Interactions of the time indicators with treatment indicator (0 for placebo, 1 for tamoxifen) will be included to allow for treatment

differences at t1 and t2, and their significance tested using a 2-df chi-square test. Low dose tamoxifen will be considered effective if 1) the 2-df test is significant and the expected RTMBD is lower both at t1 and t2 or at t2 compared to that of the placebo group, or 2) the interaction term at t2 is significant and the expected RTMBD there is lower than that of placebo. It should be noted that because common fixed effects for intercept and time coefficients are assumed for both breasts, the expected RTMBD is the same for both breasts within a treatment group. This model enables use of the data from both breasts to estimate the common treatment effect while accounting for the between-breast correlation and the correlation among repeated measurements over time within a woman. The validity of these restrictions, e.g. common intercept and treatment effect between left and right breast, while biologically reasonable, will be examined and tested. This method also enables women with incomplete RTMBD data, i.e. data from only one breast or missing data at specific time points, to be included in the analysis. In addition to the unstructured mean model, we will also fit a linear model in time, with an interaction of time by group indicator to allow for treatment difference. A significant time by group interaction, with a larger negative slope for the low dose tamoxifen group compared to placebo, will indicate the effectiveness of low dose tamoxifen in reducing MBD.

In addition to unadjusted analyses which are appropriate under the randomization principal, adjusted analysis also will be performed. Significantly imbalanced covariates and covariates known to be prognostic for BC, such as radiation dose, age at irradiation, premature menopause, and family history for BC, will be incorporated in the longitudinal models before including and testing the time by treatment group interaction.

To address potential noncompliance, we will also conduct an as-treated analysis, considering patients' actual treatment uptake. Instead of the treatment indicator (PBO or LDTAM), we will include adherence rate, i.e. 0 for PBO and a number between 0 and 1 for LDTAM determined by pill count, in the LME model. Time-specific adherence rate and the overall adherence rate will be considered. If LDTAM is effective, we may expect to see a decrease in MBD with adherence rate.

The estimates from linear mixed effects model are valid in the presence of incomplete response data if missing data occurs at random. However, non-participation and dropouts may occur differentially between treatment groups for various reasons, possibly resulting in non-ignorable missing data. In addition to collecting information on reasons for nonparticipation, we will apply two analytic approaches to examine the effects of missing data on study results [104]: 1) pattern mixture models and 2) selection models. In pattern mixture models, the four possible missing data patterns (arising from 3 time points with no missing data at t0 and considering a response as missing if data from both breasts are missing) will be used as covariates in the above-described bivariate linear mixed effects model. The effects of missing data on the estimate of treatment effect can be assessed. An overall estimate of the treatment effect may be obtained by averaging the estimates over the missing pattern groups. In selection model, we will model the probability of dropout using baseline covariates to estimate the propensity for dropout. The propensity scores will be used as a covariate in the bivariate linear mixed effects model to adjust for the effects of dropout on treatment effects.

Secondary efficacy objectives will be evaluated by applying the methods for longitudinal analysis as described below. Significance of the low dose tamoxifen effects is evaluated in the manner described above based on testing the significance of the interaction of time by group indicator variables. The distribution of continuous variables will be

examined graphically and appropriate transformations made before applying analytical methods based on normal assumption.

**Cytomorphology and proliferative index.** Samples for cytomorphology and proliferative index will be collected at two time points, at pre-treatment (t0) and at post-treatment (t2). The Masood score for cytomorphology ranges from 6 to 24, which can be classified into 4 groups of worsening morphology: 1) nonproliferative (6-10), 2) hyperplasia without atypia (11-14), 3) hyperplasia with atypia (15-18), 4) malignancy (19-24). A patient is considered to have cellular atypia if their Masood score is 15 or above. We will compare the effects of low dose tamoxifen versus placebo on changes in Masood score between pre- and post-treatment. Masood score will be treated as a continuous variable, transformed to normality as appropriate, and the linear mixed effects model applied using an indicator variable for pre- and post-treatment time points. We will also consider Masood score as an ordinal outcome with 4 categories and as a dichotomous outcome (cellular atypia or not), and apply the generalized linear mixed model (GLMM) for non-normal data [105].

Proliferative index, defined as the number of cells with unequivocal nuclear staining (Ki-67 expression) out of a total number of ductal epithelial cells contained in RPFNA samples, will be analyzed using longitudinal logistic regression with two time points. If cell counts are better approximated by a Poisson distribution, we will apply the longitudinal Poisson regression method.

**Insulin growth factors.** Insulin growth factor-1 (IGF1) and insulin growth factor binding protein-3 (IGFBP3) will be treated as continuous measures. We will apply the linear mixed effects model for between group comparisons of measures from the three time points. The unstructured mean model and linear in time model will be employed.

***Aim 2:** To establish safety and tolerability of low-dose tamoxifen.*

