These concerns led some investigators in Italy to evaluate lower doses of tamoxifen in a four-arm double-blind placebo-controlled randomized trial of 210 healthy postmenopausal women, hoping to find a dose that would be better tolerated yet still efficacious for breast cancer risk reduction [41]. Participants were randomized to one of four treatment arms: 1) tamoxifen at 1 mg/day and a weekly placebo, 2) a daily placebo and tamoxifen at 10 mg/week, 3) tamoxifen at 5 mg/day and a weekly placebo, or 4) both daily and weekly placebos for 12 months. Plasma insulin-like growth factor 1 (IGF-1), which is positively correlated with BC risk, was the primary endpoint, evaluated before and after the 12-month treatment. Secondary endpoints included MBD, IGF binding protein-3 (IGFBP-3), fibrinogen, antithrombin-III (AT3), C-telopeptide (CTX), and endometrial proliferation assessed by Pipelle biopsy. MBD is positively correlated with BC risk, while IGFBP-3 is negatively correlated with BC risk. Along with IGF-1, they served as surrogate endpoints of efficacy. Fibrinogen and AT3 are markers of clotting risk, CTX, which is positively correlated with bone resorptive activity, is a marker for osteoporosis risk, and endometrial proliferation is a marker of uterine cancer risk. Collectively, these were safety endpoints in the trial. The investigators reported a significant decrease in IGF-1 in all tamoxifen arms relative to placebo ( $p = 0.005$ ), with the greatest change observed in the 5 mg/day treatment arm ( $p = 0.019$ ). Low-dose tamoxifen also lowered MBD and increased IGFBP-3, with optimal effects observed in the 5 mg/day arm. These findings all consistently suggest that 5 mg/day dosing is the most effective dose schedule of low-dose tamoxifen. No significant change was observed with CTX, suggesting that low-dose tamoxifen does not adversely affect bone health. Interestingly, a significant decrease in AT3 ( $p = 0.006$ ), particularly with the 5 mg/day dose schedule, was also seen, suggesting that low-dose tamoxifen may be associated with a lower clotting risk than even placebo. While there was an association between low-dose tamoxifen and endometrial thickness, no association was found with endometrial proliferation measured with Ki67 expression. In fact, Ki67 was lowest in patients receiving the 5 mg/day dose, suggesting that low-dose tamoxifen at that dose would likely not be associated with an increased risk of endometrial carcinoma as is observed with standard dose tamoxifen. Also, menopausal symptoms were not

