## 12.5 Power and sample size:

***Aim 1:*** *To determine the impact of low-dose tamoxifen on surrogate endpoint biomarkers of BC risk.*

**Mammographic breast density (MBD):** The primary efficacy endpoint of the trial is MBD. The efficacy of low dose tamoxifen will be examined by comparing the slopes in the longitudinal linear regression of the MBD on time since treatment initiation between the low dose tamoxifen group and placebo control group. For sample size calculation, we let Y, the response, as the mean of the square root of MBD (RTMBD) from both breasts. Because of randomization, we expect no difference between the expected values of Y at t0 between treatments but expect the linear slopes of the two groups to diverge over time, if the intervention is efficacious. Power/sample size calculation was conducted by assuming a linear change in RTMBD over time and various magnitudes of RTMBD difference expected at t2 between the treatment and control groups.

Longitudinal power calculation requires specification of the expected linear trend (thus the expected values of Y at t0, t1, t2) for the controls, the variance/covariance of the repeated measurements, the expected difference in Y at t2 between the treatment groups, and the correlations among repeated measurements. These estimates were obtained from 41 control women in the Puget Sound NSABP P-1 participating sites, [106] 16 pre-menopausal women (median age=50, range=38-50) and 25 post-menopausal women, (median age=57, range=36-74), with data on MBD expressed as a percent breast density at pre-, 1-yr, and 2-yr post-treatment. Although this entire control sample (median age=50, range=36-74) is older than the available CPIR HL cohort (median age=35, range 25-50), based on changes in MBD observed with hormonal fluctuations during the menstrual cycle [66] and after discontinuation of exogenous hormone in postmenopausal women [70], it can be reasonably assumed that estrogen withdrawal associated with menopause has a greater impact on variation in MBD than age alone. Thus, we assumed that the estimates obtained from these women can be applied to the anticipated CAYAC patient control sample.

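### The primary efficacy rule in section 12.4 accepts either of two tests with no stated or shared alpha: at two-sided 0.05 each, the chance of a false claim of benefit is 3.76%, not 2.5%

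*Combined protocol and SAP*

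**What the plan says.** Section 12.4 (Aim 1, mammographic breast density, MBD) fits a mixed model to square-root MBD (RTMBD), with treatment interactions at year 1 (t1) and year 2 (t2). Two numbered routes, joined by an or, lead to a conclusion of effectiveness.

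- Route 1: "the 2-df test is significant and the expected RTMBD is lower both at t1 and t2 or at t2 compared" with placebo.
- Route 2: "the interaction term at t2 is significant and the expected RTMBD there is lower than that of placebo".

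The same section then adds a slope analysis: "In addition to the unstructured mean model, we will also fit a linear model in time". Of this it says: "A significant time by group interaction, with a larger negative slope for the low dose tamoxifen group compared to placebo, will indicate the effectiveness" of the drug.

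On the covariance it says: "Unstructured and compound symmetry covariance structures will be considered for residual errors".

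Section 12.4 states no alpha for any of these tests. Section 12.5 does, for sizing: "We assumed a Type I error of .05, power of .80, 2-sided test". That level belongs to a different single test: "The efficacy of low dose tamoxifen will be examined by comparing the slopes in the longitudinal linear regression of the MBD on time".

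**The concern.** The direction condition in route 1 is looser than it looks. Lower at both visits, or lower at year 2, is logically the same as lower at year 2. Route 1 therefore needs a significant joint test and a year-2 estimate below placebo by any amount. Year 1 may lie in either direction.

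Two overlapping tests, each sufficient, give two chances of a positive result. If each is run at full level, the rule does not keep the 2.5% favourable-direction error implied by a two-sided 0.05 test. The slope statement leaves open whether there is a third chance. The trial was sized on the slope, but the numbered criteria do not use it. This rule decides whether the trial is positive.

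**Working it through.** **Inputs.** From section 12.5: two-sided 0.05, 80% power, correlation 0.8 with compound symmetry, effect 0.25 SD at year 2, 100 per arm, 115 per arm with 10% attrition at each annual visit. Assumption: each route in section 12.4 is tested at that 0.05.

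**1. The plan's own figure.** With three equally spaced visits, compound symmetry and complete data, the slope estimate is half the t2 minus t0 contrast, so the slope test is the year-2 interaction test. The variance of a woman's change is 2(1 − 0.8) = 0.4 SD².

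- n per arm = 2(1.960 + 0.842)² × 0.4 / 0.25² = 100.5 (plan: 100).
- SE at 100 per arm = √(2 × 0.4/100) = 0.0894 SD. Power = Φ(0.25/0.0894 − 1.960) = 79.8% (plan: 80%).
- With 115 per arm and 10% attrition per visit, generalised least squares gives 78.6%.

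The sizing reproduces, for one test.

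**2. False claim under no effect, two numbered routes.** Let z₂ be the year-2 interaction statistic. The 2-df statistic equals z₂² + w², where w is the part of the year-1 interaction independent of z₂. Under the null, w is standard normal, so the correlation between visits drops out. The 5% critical value is 5.991.

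P(claim) = 0.025 + ∫ from −1.96 to 0 of φ(z) P(χ²₁ > 5.991 − z²) dz = 0.025 + 0.0126 = **0.0376**.

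Simulation under compound symmetry, AR(1) and an unstructured covariance gave 3.75%, 3.73% and 3.76%. Requiring a lower estimate at both visits in route 1, with levels unchanged, still leaves about 3.1%.

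**3. Adding the slope as a route.** Complete data and compound symmetry: no change, by step 1. Under unstructured covariances the slope is no longer the t2 minus t0 contrast. Three assumed correlation sets, not from the documents, in the order t0–t1, t1–t2, t0–t2:

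| Correlations | False claim |
|---|---|
| .85 / .80 / .75 | 4.0% |
| .75 / .85 / .80 | 4.2% |
| .80 / .90 / .80 | 4.3% |

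**4. A difference at year 1 only, none at year 2.** Take 100 per arm and correlation 0.8 between visits, so the two interactions correlate 0.5. If the year-1 difference is k SE, w has mean ±k/√(1 − 0.5²) = ±1.155k. The step 2 integral is then taken with this shifted w. One SE is 0.09 SD and two are 0.18 SD. The result depends on what lower means.

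| Reading of lower at year 2 | 1 SE | 2 SE |
|---|---|---|
| Sign of the interaction (rise or vanished reduction) | 9.0% | 26.8% |
| Model group mean, year-1 rise | 10.4% | 29.5% |
| Model group mean, reduction gone by year 2 | 7.5% | 24.0% |
| Year-2 interaction test alone, by interaction sign | 2.5% | 2.5% |

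The group-mean rows differ because section 12.4 lets the intercept vary by arm, so a chance baseline difference enters the year-2 mean. They come from 4,000,000 simulated trials. In the first row, correlations of 0.3 to 0.7 between the interactions give 8.0% to 11.8% and 22.9% to 35.5%.

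**5. Power at 0.25 SD, 100 per arm, complete data.**

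| Rule | Linear effect | Full effect by year 1 |
|---|---|---|
| Current rule, interaction sign | 81.1% | 87.4% |
| Current rule, group mean | 78.8% | 84.5% |
| Year-2 interaction alone, 0.05 | 79.8% | 79.8% |
| Both routes at 0.0328 | 75.9% | 83.3% |

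The level 0.0328 solves step 2 for a total of 2.50%.

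**The case against.** The best defence has four parts.

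- *Alpha is stated.* Section 12.5 gives 0.05, and the plan makes one claim, wrongly in 3.76% of null trials, which is below 0.05. This stands in part: the level is in the documents, and 0.05 per route is an assumption about how section 12.4 would be applied. But a two-sided 0.05 test allows 2.5% in the direction of benefit, and nothing says how the routes share it.
- *The 2-df test has a purpose.* It gains power if density falls early, and section 2.4 reports decreases after 1 to 2 years of treatment. This stands, and it is the real cost of dropping route 1.
- *The year-1 figures are not type I errors of the 2-df test.* Its null is no difference at either visit, and density is measured at both. This stands. A reader might take the 9% and 27% as false-positive rates; they describe how often the rule says effective when nothing remains at year 2. Nor do the documents predict a rise: section 2.2 says "Low-dose tamoxifen also lowered MBD and increased IGFBP-3".
- *The slope analysis is an addition.* A reader might infer three co-primary tests and an error of 4.0% to 4.3%. The documents do not establish that: the slope is introduced as a further model, and those rates rest on assumed matrices. Equally, it cannot be said without qualification that the slope adds nothing.

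**Conclusion.** The point holds. With each numbered route at two-sided 0.05, the rule gives 3.76% false claims of benefit against 2.5%, an excess of 1.26 points that does not depend on the correlation between visits or, under the null, on the reading of lower. If the slope also counts, 3.76% is a minimum: unchanged under compound symmetry with complete data, and about 4.0% to 4.3% under the illustrative unstructured forms. Route 1 also lets a year-1 difference carry the claim when the year-2 estimate is only trivially below placebo.

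The excess is modest, for a Phase IIb trial on a surrogate endpoint. A reader might infer that the trial is undersized or that a positive result could not be trusted; the documents support neither. The stated sizing reproduces, and the two tests overlap heavily. The defect is that the decision rule does not have the error rate used for sizing. It should be fixed because it governs the primary conclusion and the repair is cheap.

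**What to change.** Before unblinding, amend sections 12.4 and 12.5.

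1. In 12.4, name one primary test at two-sided 0.05. A natural choice is the treatment-by-year-2 interaction, with a lower value on tamoxifen. Under compound symmetry and complete data it is the same test as the sizing slope, with 79.8% power at 100 per arm.
2. State that the 2-df and slope tests are supportive, and make the efficacy statement in 12.5 agree.
3. Define lower as the sign of the interaction, that is, the difference in change from baseline, and not as the raw group mean.

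The cost is wording plus some power. Against the current rule read by interaction sign, power falls by about 1 point for a linear effect (81.1% to 79.8%) and about 8 points if the full effect is present at year 1 (87.4% to 79.8%).

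If the team values the early-effect power and wants both routes, it should state levels that hold the overall favourable-direction error at 2.5%, for example about 0.0328 two-sided for each, with the slope supportive. That gives 75.9% and 83.3% in the same two scenarios. The choice is the team's; it needs to be written down.
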